### 8.2.5 Sponsor Responsibility for Reporting Adverse Events

All Adverse Events will be reported to regulatory authorities, IRB/IECs and investigators in accordance with all applicable global laws and regulations.

## 9.0 STATISTICAL ANALYSIS PLAN

### 9.1 Statistical Analysis Plan Summary

Data analyses will be primarily descriptive in nature. Descriptive statistics will be presented for safety, pharmacodynamic, and exploratory endpoints. For categorical variables, summary tabulations of the number and percentage within each category (with a category for missing data, if applicable) of the parameter will be presented. For continuous variables, data will be presented as number (n), mean, median, standard deviation, and range (minimum and maximum). Discrete variables will be presented as frequencies or proportions. No formal statistical comparisons between dose groups will be performed. Data from all investigational sites will be pooled in the summary tables and analyses. Data collected on patients who are screen failures will not be included in any summary tables, listings, or analyses.

A detailed statistical analysis plan (SAP) will be finalized before database lock and will document the analysis methods, data handling procedures, and other statistical analysis issues.

### 9.2 Efficacy and Toxicity Analysis

The primary statistical analysis is based on the Bayesian optimal interval design (BOIN12) of Lin et al. (Lin et al., 2020). An adaptive escalation schema (see Section 2.1.2) is used to find a dose with optimal clinical efficacy and acceptable toxicity. The design has a minimum sample size of 3 patients and a maximum of 21. The operating characteristics of the design were estimated from 10,000 trials simulated with the BOIN12 shiny app (V1.5.2.0) available at <http://www.trialdesign.org>. True efficacy rate of 0.50 and toxicity rates 0.30 or lower are deemed to be clinically desirable. Efficacy of 0.10 or less is uninteresting clinically. The trial design has 36% and 49% probabilities (85% total power, 15.6 expected number of patients treated) of selecting dose 7.5 mg or 10 mg if their efficacy rates are 0.40 and 0.50, respectively, and their toxicity rates are both 0.20. The selection probabilities decrease to 70%, 47%, and 24% at higher toxicity rates of 0.30, 0.40, and 0.50. Conversely, the design has a total selection probability of 3% (type I error, 7.9 expected number of treated patients) at efficacy rates of 0.10 and toxicity rates of 0.20. Selection probabilities and expected numbers of treated patients for these and other true efficacy and toxicity rate scenarios are summarized in Table B of APPENDIX F.

### 9.3 Analysis Populations

Study populations will be defined as follows:

- Safety and Efficacy Population: all subjects who receive at least 1 dose of CMP-001 and at least 1 recorded post-baseline assessment of objective response, assessed according to Cheson 2007 criteria.

- Pharmacodynamic Population: All subjects receiving any amount of study medication (placebo or active) and having any measurable IP-10 data.

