### 2.1.3 Dose-Limiting Toxicities

The DLT observation period is 15 days from date of first (W1D1) CMP-001 injection (i.e., following 3 doses of CMP-001; W1D1, W2D1, W3D1). Subjects who have received at least one dose of CMP-001 and pembrolizumab are evaluable for DLT assessments.

DLTs are defined below and only include AEs that are considered possibly, probably, or definitely related to the CMP-001 plus pembrolizumab combination. Attribution of AEs specifically to either CMP-001 or pembrolizumab is challenging, therefore, the relationship to CMP-001 should be based on attribution to the combination of the two study drugs (CMP-001 + pembrolizumab).

The following AEs will be considered DLTs **if deemed related to study drug combination**:

- Hematologic
  - Grade 4 neutropenia
  - Febrile neutropenia, defined as absolute neutrophil count (ANC) <1000/mm^3 with a temperature of  $\geq 38.3$  degrees C
  - Grade  $\geq 3$  neutropenic infection
  - Grade  $\geq 3$  thrombocytopenia with clinically significant bleeding seeking medical intervention
  - Grade 4 thrombocytopenia
- Non-hematologic:
  - Grade  $\geq 3$  toxicities (non-laboratory); excluding:
    - Grade 3 fatigue lasting <7 days
    - Grade 3 arthralgia or myalgia that downgrades to less or equal to grade 2 within 3 days of supportive care
    - Grade 3 pain at injection site that downgrades to less than or equal to Grade 2 within 3 days of supportive care

- Grade 3 electrolyte abnormalities that are asymptomatic and reversed with medical intervention within 3 days
  - Grade  $\geq 3$  nausea, vomiting or diarrhea despite maximal medical intervention
  - Grade 4 aspartate aminotransferase (AST) and alanine aminotransferase (ALT) unless alternate explanations such as viral hepatitis or disease progression in the liver
- Other (non- AST/ALT) non-hematologic Grade  $\geq 3$  laboratory value if the abnormality leads to overnight hospitalization

[figure not shown]
[figure not shown]

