Subjects discontinuing study treatment earlier than planned or withdrawing from the study should undergo the End of Treatment (EOT) clinical and laboratory assessments (see Section 7.0 TRIAL FLOW CHART) as soon as possible after study treatment is stopped. The required 30 day follow-up phone call should also be completed. The reason for withdrawal will be recorded in the electronic case report form (eCRF) and the subject's source medical record.

If a subject withdraws from the study prior to completion of the 21 day assessment period for a reason other than a DLT, then a replacement subject will be enrolled at that dose level.

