- i. Blood samples (20 ml) for research including exploratory biomarker, immunogenicity studies, and assessment of pharmacodynamics are to be collected at screening and then on following days and times:  
 Blood draw pre-treatment W1D1 or before, W3D1, W6D1, W10D1 prior to dosing with CMP-001 – Additional blood draw with subsequent cycles may be requested.
- j. Archival tumor samples should be identified at Screening, if available for potential access later. Additional tumor biopsies are optional and may be collected at other times then specified below at the discretion of the Investigator. Optional tumor biopsies (fresh frozen when feasible and typically FNA), will be collected prior to starting treatment on W1D1, W3D1, W6D1, W10D1. If pre-treatment biopsy prior to W1D1 treatment not done, it can be scheduled with W2D1 intra-tumor injection.
- k. In women of childbearing age, Urine pregnancy testing should be performed at Screening and prior to 1st CMP-001 injection (W1D1), prior to 4th CMP-001 injection (W4D1), prior to 7th CMP-001 injection (W7D1), followed by every 3 weeks prior to treatment and EOT. A negative test within 72 hours of treatment is acceptable.
- l. CT neck/chest/abdomen/pelvis with contrast or PET-CT scans to assess response will be at W7D1 (or after two cycles) and then as clinically indicated. Subjects may be asked to provide historical scans (scans performed prior to Screening) for informational purposes prior to starting CMP-001 therapy, if available.
- m. The first CMP-001 injection stimulates antibody formation to the VLP of CMP-001 and will be given subcutaneously. Subsequently, CMP-001 should be administered as close to the tumor as possible if intratumoral injection not possible. A window of  $\pm 2$  day is permitted for the CMP-001 dose schedule for the first weekly CMP-001 injections and a window of  $\pm 7$  days is permitted for every 3 week CMP-001 injections. To assure maximum effectiveness, consecutive IT injections of CMP-001 should always be administered at least 96 hours apart. No CMP-001 dose should be skipped. If a CMP-001 dose needs to be delayed due to toxicity the dose should be completed as soon as the toxicity has resolved.

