## 9.5 Demographics and Other Baseline Characteristics

Demographics and other baseline characteristics (age, sex, race, body weight, height, and BMI) will be summarized for each dose group using descriptive statistics (number of subjects, mean, standard deviation, median, minimum, and maximum for continuous variables, and the number and percentage of subjects for categorical variables) for the Safety Population.

Cancer History: At Screening, lymphoma and any other cancer type history will be obtained, and will include date of diagnosis, and prior and concomitant therapies. Lymphoma history (age at diagnosis, duration of disease, prior treatments, and location of tumors) will be summarized by dose group using descriptive statistics for the Safety Population, and listed by subject.

Medical and Surgical History: Medical and surgical history (excluding lymphoma history) will be listed by subject. Medical history will be coded using the most recent version of the MedDRA available at the time of study start.

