## APPENDIX F. BOIN12 TRIAL DESIGN CHARACTERISTICS

**Table A.** Rank-based desirability score (RDS) table for the BOIN12 design, where “E” means elimination. A larger value of RDS means higher desirability, and any value of RDS is deemed higher than “E”. #Pts denotes the number of evaluable patients treated at current dose; #Tox denotes the number of evaluable patients who experience toxicity; #Eff denotes the number of evaluable patients who experience efficacy.

#Pts	#Tox	#Eff	RDS	#Pts	#Tox	#Eff	RDS	#Pts	#Tox	#Eff	RDS	#Pts	#Tox	#Eff	RDS
0	0	0	62	6	3	5	74	9	4	3	4	12	2	11	106
3	0	<= 0	E	6	3	6	93	9	4	4	15	12	2	12	116
3	0	1	42	6	>= 4	Any	E	9	4	5	33	12	3	<= 3	E
3	0	2	69	9	0	<= 2	E	9	4	6	48	12	3	4	3
3	0	3	96	9	0	3	19	9	4	7	67	12	3	5	12
3	1	<= 0	E	9	0	4	36	9	4	8	84	12	3	6	26
3	1	1	34	9	0	5	54	9	4	9	102	12	3	7	41
3	1	2	60	9	0	6	72	9	>= 5	Any	E	12	3	8	57
3	1	3	88	9	0	7	89	12	0	<= 3	E	12	3	9	73
3	2	<= 0	E	9	0	8	104	12	0	4	11	12	3	10	87
3	2	1	27	9	0	9	117	12	0	5	24	12	3	11	103
3	2	2	53	9	1	<= 2	E	12	0	6	40	12	3	12	114
3	2	3	80	9	1	3	14	12	0	7	56	12	4	<= 3	E
3	>= 3	Any	E	9	1	4	30	12	0	8	71	12	4	4	2
6	0	<= 1	E	9	1	5	47	12	0	9	86	12	4	5	9
6	0	2	28	9	1	6	65	12	0	10	101	12	4	6	22
6	0	3	49	9	1	7	82	12	0	11	113	12	4	7	37
6	0	4	70	9	1	8	100	12	0	12	119	12	4	8	52
6	0	5	91	9	1	9	115	12	1	<= 3	E	12	4	9	68
6	0	6	110	9	2	<= 2	E	12	1	4	8	12	4	10	83
6	1	<= 1	E	9	2	3	10	12	1	5	20	12	4	11	98
6	1	2	23	9	2	4	25	12	1	6	35	12	4	12	112
6	1	3	44	9	2	5	43	12	1	7	50	12	5	<= 3	E
6	1	4	64	9	2	6	59	12	1	8	66	12	5	4	1
6	1	5	85	9	2	7	77	12	1	9	81	12	5	5	6
6	1	6	105	9	2	8	95	12	1	10	97	12	5	6	17
6	2	<= 1	E	9	2	9	111	12	1	11	109	12	5	7	32
6	2	2	18	9	3	<= 2	E	12	1	12	118	12	5	8	46
6	2	3	39	9	3	3	7	12	2	<= 3	E	12	5	9	63
6	2	4	58	9	3	4	21	12	2	4	5	12	5	10	78
6	2	5	79	9	3	5	38	12	2	5	16	12	5	11	94
6	2	6	99	9	3	6	55	12	2	6	29	12	5	12	108
6	3	<= 1	E	9	3	7	75	12	2	7	45	12	>= 6	Any	E
6	3	2	13	9	3	8	90	12	2	8	61				
6	3	3	31	9	3	9	107	12	2	9	76				
6	3	4	51	9	4	<= 2	E	12	2	10	92				

**Table B.** Operating characteristics of the BOIN12 design.

	CMP-001 Dose Level		Stop %
	7.5 mg	10 mg	
Scenario 1			
DLT rate	0.2	0.2	
Efficacy rate	0.1	0.1	
No. Pts treated	4.2	3.7	
Select %	1.9	1.2	96.9
Scenario 2			
DLT rate	0.2	0.2	
Efficacy rate	0.1	0.2	
No. Pts treated	4.2	5.2	
Select %	2.3	10.7	87
Scenario 3			
DLT rate	0.2	0.2	
Efficacy rate	0.2	0.3	
No. Pts treated	5.7	6.5	
Select %	12.4	26.1	61.5
Scenario 4			
DLT rate	0.2	0.2	
Efficacy rate	0.3	0.4	
No. Pts treated	6.8	7.5	

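### The only defined safety set also requires a recorded response assessment, so dosed patients who leave unassessed drop out of it and out of the response-rate denominator

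*Combined protocol and SAP*

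**What the plan says.** Section 9.3 defines a joint Safety and Efficacy Population as "all subjects who receive at least 1 dose of CMP-001 and at least 1 recorded post-baseline assessment of objective response", judged by Cheson 2007. The only other set is pharmacodynamic. Section 9.5 nevertheless refers to a safety population by name: lymphoma history "will be summarized by dose group using descriptive statistics for the Safety Population, and listed by subject".

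Footnote l of the Trial Flow Chart (Section 7.0) says that response scans "will be at W7D1 (or after two cycles) and then as clinically indicated". The chart marks no disease assessment at the end-of-treatment visit.

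Section 5.5 sets this condition for replacement: "If a subject withdraws from the study prior to completion of the 21 day assessment period for a reason other than a DLT". The consequence attached to that condition is as follows: "then a replacement subject will be enrolled at that dose level". On toxicity, Section 2.1.3 states: "Subjects who have received at least one dose of CMP-001 and pembrolizumab are evaluable for DLT assessments". It also states: "The DLT observation period is 15 days from date of first (W1D1) CMP-001 injection".

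On dose decisions, the note to Table A in Appendix F says: "Pts denotes the number of evaluable patients treated at current dose". Section 2.1.2 requires a cohort to be evaluable for efficacy and for DLT before the next is treated, and Section 1.0 caps the trial at 21 evaluable patients. None of these places says what makes a patient evaluable for efficacy.

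Under inclusion criterion 8 (Section 5.1), some patients with few B cells receive the priming dose and continue only if they make anti-Qbeta antibody.

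**The concern.** Membership of the set depends on what happens after dosing. W7D1 is day 43 (6 × 7 + 1). A patient who is dosed and then dies, stops for toxicity or deteriorates clinically before anyone records a response assessment meets the first half of the definition but not the second. Patients given only the priming dose would normally be in the same position.

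Two results suffer. ORR loses patients who are mostly non-responders, so it is biased upward. Any safety summary based on the 9.3 set loses patients selected for having left early, so early toxicity can be understated. Appendix E places the trial in its highest risk level, which makes a safety set conditional on reaching an assessment hard to defend.

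Dose decisions may be affected on the efficacy side. Section 5.5 replaces those who withdraw before day 21 for any reason but a DLT and does not except progression. With efficacy evaluability undefined, early non-responders can be left out of #Eff/#Pts.

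**Working it through.** **1. Which early leavers are lost, and where**

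| Patient with no recorded assessment | 9.3 set (safety and ORR) | BOIN12 toxicity count | BOIN12 efficacy count |
|---|---|---|---|
| DLT, then leaves | out | in, if dosed with both drugs (2.1.3); not replaced (5.5) | not stated |
| Withdraws before day 21, no DLT | out | 2.1.3 makes the patient evaluable if dosed with both drugs, yet 5.5 replaces | replaced; otherwise not stated |
| Leaves between day 21 and W7D1 | out | in, if dosed with both drugs | not stated; 5.5 does not apply |
| Priming dose only | normally out | not stated | not stated |

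**2. Reproducing the plan's figures**

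Inputs from Section 2.1.2: cohorts of 3, maximum 21, stop at 12 on a dose, utility E − 0.3T, and admissibility limits 0.3 (cutoff 0.925) and 0.5 (cutoff 0.90). Assumed: Beta(1,1) priors, and interval boundaries 0.236/0.359 with a switch at 6 patients, because the decision table is not shown in the text available.

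- Efficacy 0.40/0.50, DLT 0.20/0.20: simulated total selection 84.7%, expected N 15.1. Section 9.2 states 85% and 15.6.
- Efficacy 0.10/0.10, DLT 0.20/0.20: simulated 3.0%, expected N 7.9. Section 9.2 states 3% and 7.9.
- The elimination boundaries of Table A match exactly.

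The design figures are sound for patients who count as evaluable. The open question is who counts.

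**3. Effect on ORR**

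Let p be the true ORR in all treated patients and d the share dropped as unassessed non-responders. The reported ORR is p/(1 − d).

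- p = 0.25: 0.25/0.90 = 0.278; 0.25/0.80 = 0.3125.
- p = 0.40, d = 0.20: 0.40/0.80 = 0.50, the rate that Section 9.2 calls desirable.

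**4. Effect on dose selection, if the same patients are also left out of Table A**

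True ORR 0.25 on both doses, DLT rate 0.20 on both:

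| d | Efficacy rate seen | Total selection, exact enumeration | Total selection, simulation |
|---|---|---|---|
| 0 | 0.25 | 36.8% | 38% |
| 0.10 | 0.278 | 45.4% | 46% |
| 0.20 | 0.3125 | 55.8% | 57% |

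**5. One dose, by hand**

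With a Beta(1,1) prior, Pr(π_E < 0.5) for x responders in n equals Pr(Bin(n + 1, 0.5) ≥ x + 1).

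- 3 of 12: 1 − (1 + 13 + 78 + 286)/8192 = 0.954, above 0.90, so the dose is eliminated.
- The same 12 patients with three unassessed non-responders dropped, 3 of 9: 1 − (1 + 10 + 45 + 120)/1024 = 0.828, so the dose stays admissible.

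Table A agrees: 3 or fewer responders in 12 is E, while 3 in 9 has a score for 0 to 4 toxicities.

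**6. Effect on a safety summary**

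Suppose the true DLT rate is 0.20, half of the patients with a DLT leave unassessed, and everyone else is assessed. The rate in the 9.3 set is 0.10/(0.10 + 0.80) = 0.111. The share of one half is an assumption.

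**The case against.** A reader might infer that early toxicity disappears from dose selection. It does not. Section 2.1.3 asks for one dose of each drug and no response assessment, and Section 5.5 does not replace patients who leave with a DLT. Replacing only DLT-free leavers would, if anything, raise the observed DLT rate.

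A reader might also infer that every event in a patient without a Week 7 scan is lost. That is too strong. Section 8.2 requires all AEs from W1D1 to be reported, Section 9.4 tabulates disposition for all dosed patients, and Appendix E has cumulative AE review. Section 9.5 applies the safety population by name only to baseline tables. The definition also asks for an assessment, not the Week 7 scan. An earlier scan or, for superficial cutaneous lesions, a caliper measurement (Section 8.1.3) keeps the patient in, and progression recorded that way counts as non-response.

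Nor do the documents say that early failures are excluded from Table A. No text links Table A to the 9.3 set. Whether a rapid progressor is replaced is also unclear: Section 5.5 has patients stop treatment but remain monitored, while Section 1.0 takes progressing patients off study.

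The size of the effect is assumed too. If 20% leave unassessed but half do so after day 21 and are counted as non-responders, selection rises to about 45%, not 56%. The handling of priming-only patients refers to a trial schema whose figure is not in the text available.

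These points narrow the concern. None changes the 9.3 definition. The detailed SAP promised in Section 9.1 is due before database lock, which may be too late for cohort decisions made during accrual.

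**Conclusion.** The definition in Section 9.3 is wrong as written and can be corrected by wording. Dosed patients with no recorded post-baseline assessment are outside the only defined safety set and outside the ORR denominator. The bias in ORR is upward when those patients are mainly non-responders. Early toxicity can be understated in any summary that uses the set.

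For dose decisions the supportable statement is that efficacy evaluability is undefined and that the replacement rule does not except progression, so early non-responders may be left out.

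The rise in total selection from about 37% to 45% (10% dropped) or 56% (20% dropped) is an illustration. It rests on a true ORR of 0.25 on both doses, DLT rates of 0.20, assumed boundaries of 0.236/0.359, an assumed dropout rate, and all dropped patients being non-responders who are missing from Table A.

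**What to change.** 1. Define the safety population as all subjects who receive any dose of either study drug.
2. Define the response population as all who start study treatment at a dose level, with no post-baseline assessment counted as non-response. Report evaluable-only ORR as supportive. State how priming-only patients are counted.
3. For the BOIN12 efficacy count, state that patients who leave before W7D1 because of progression, death or toxicity count as #Eff = 0. Handle DLT evaluability separately: Table A uses one #Pts for both outcomes, so entering a patient with an incomplete DLT window as #Tox = 0 would dilute the toxicity rate.
4. Limit replacement to withdrawals unrelated to disease or treatment, and tabulate replaced patients. Reconcile the 15-day DLT window in Section 2.1.3 with the 21-day assessment period in Section 5.5.

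Cost: a protocol wording change while accrual is under way, which alters who counts toward the 21, and a slightly lower reported ORR and selection probability. The rates in Table B need not change, but its efficacy rates should then be read as rates among all treated patients.

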## 9.4 Disposition

The number and percentage of subjects who enroll into the study (sign informed consent), who are dosed with CMP-001, and who discontinue, and the primary reason for discontinuation will be summarized by dose group.

Study completion information, including the reason for study withdrawal, if applicable, will be presented in a by-subject data listing.

## 9.5 Demographics and Other Baseline Characteristics

Demographics and other baseline characteristics (age, sex, race, body weight, height, and BMI) will be summarized for each dose group using descriptive statistics (number of subjects, mean, standard deviation, median, minimum, and maximum for continuous variables, and the number and percentage of subjects for categorical variables) for the Safety Population.

Cancer History: At Screening, lymphoma and any other cancer type history will be obtained, and will include date of diagnosis, and prior and concomitant therapies. Lymphoma history (age at diagnosis, duration of disease, prior treatments, and location of tumors) will be summarized by dose group using descriptive statistics for the Safety Population, and listed by subject.

Medical and Surgical History: Medical and surgical history (excluding lymphoma history) will be listed by subject. Medical history will be coded using the most recent version of the MedDRA available at the time of study start.

## 9.6 Protocol Deviations

Protocol deviations (including but not limited to failure to meet study eligibility criteria, use of disallowed concomitant medications, and study drug overdoses) will be presented by subject in a by-subject data listing. Prior to database lock all deviations will be reviewed and classified as major or minor.

## 10.0 LABELING, PACKAGING, STORAGE AND RETURN OF CLINICAL SUPPLIES

### 10.1 Investigational Product

The investigator shall take responsibility for and shall take all steps to maintain appropriate records and ensure appropriate supply, storage, handling, distribution, and usage of investigational product in accordance with the protocol and any applicable laws and regulations.

CMP-001 drug product is supplied as a 5 mg/ml concentration. CMP-001 is a colorless to pale yellow/brown opalescent liquid.

NOTE: CMP-001 may require a dilution at the investigational site to a 1.0 mg/mL using normal saline (refer to Pharmacy Manual for diluting instructions). **Table 5**

Pembrolizumab will be provided by Merck as summarized in Table 11.

**Table 11 Product Descriptions**

Product Name & Potency	Dosage Form
Pembrolizumab 100 mg/ 4mL	Solution for Injection

## 10.2 Packaging and Labeling Information

Supplies will be labeled in accordance with regulatory requirements.

## 10.3 Clinical Supplies Disclosure

This trial is open-label; therefore, the participant, the trial site personnel, the Sponsor and/or designee are not blinded to treatment. Drug identity (name, strength) is included in the label text; random code/disclosure envelopes or lists are not provided.

